The aim of the study is to assess the impact of CKD status on the PK and PD profile of ticagrelor among patients with DM and CAD. Moreover, how DM and CKD status can affect PK/PD profiles in patients treated with different dosing regimens of ticagrelor (60mg and 90 mg) will also be assessed.

Study Population

The study will be performed at the University of Florida Health Science Center at UF Health Jacksonville - Division of Cardiology. Patients will be recruited in the Cardiology Clinics of our institution and will be screened by Cardiology Research staff, who will verify that all candidates meet inclusion and exclusion criteria. Results from blood tests performed within the last 90 days will be considered valid for screening purposes. If these are not available, a blood sample will be collected for the screening phase. The research design will have common inclusion and exclusion criteria as described below.

Inclusion criteria:

- Age >18 years.
- Type 2 DM, defined according to WHO definition, on treatment with oral hypoglycemic agents and/or insulin for at least 2 months without any changes in treatment regimen;
- Angiographically documented CAD.
- On treatment with low-dose aspirin (81mg/day) and clopidogrel (75mg/day) for at least 30 days as part of standard of care.

Exclusion criteria:

- Patients with end-stage renal disease on hemodialysis.
- Use of any antiplatelet therapy (except aspirin and clopidogrel) in past 30 days.
- Use of parenteral or oral anticoagulation in past 30 day.
- Active pathological bleeding.
- History of intracranial hemorrhage with prior hemorrhage stroke.
- Blood dyscrasia or bleeding diathesis.
- Any active malignancy.
- Platelet count < $80 \times 10^6 / \mu\text{l}$.
- Hemoglobin <8 g/dl.
- Known hepatic dysfunction (known moderate and severe hepatic dysfunction).
- Hemodynamic instability.
- Known allergy or hypersensitivity to ticagrelor or any excipients.
- Pregnant / lactating females (women of childbearing age must use reliable birth control while in the study).

- Strong inhibitors of cytochrome CYP3A4 and potent inducers of cytochrome CYP3A4 (to avoid interaction with ticagrelor): ketoconazole, itraconazole, voriconazole, clarithromycin, nefazodone, ritonavir, saquinavir, nelfinavir, indinavir, atazanavir and telithromizycin.
- Patients with sick sinus syndrome (SSS) or high degree AV block without pacemaker protection.

Research design

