- A. standard dose (90mg twice daily of ticagrelor) for 7-10 days (phase 1) and then cross-over to low dose (60mg twice daily of ticagrelor) for 7-10 days (phase 2)
- B. low dose (60mg twice daily of ticagrelor) for 7-10 days (phase 1) and then cross-over to standard dose (90mg twice daily of ticagrelor) for 7-10 days (phase 2).

After the 2 phases of treatment (maximal treatment period 20 days) patients will resume their standard DAPT with aspirin and clopidogrel (end of study treatment).

[figure not shown]
After 7-10 days of treatment, patients will come for their blood sampling in the morning hours. In particular, patients will not assume their scheduled morning dose of study medication to allow assessment of trough levels of platelet reactivity. Patients will be administered the dose of the randomized treatment while at the clinic and blood sampling will be collected after 2 hours

in order to assess peak levels of platelet reactivity. After completing the first phase of the randomized assignment, patients will initiate the second phase and start assuming assigned medication 12 hours the last dose.

Blood for sampling will be collected at the following visits (a total of 5 assessments at 3 visits):

- a) baseline (24 hours after last clopidogrel MD): PD assessments
- b) after 7-10 days of ticagrelor therapy (phase 1-pre-crossover): PK and PD assessment will be assessed to define trough (12 ± 2 hours after last ticagrelor dose) and peak (2 hours after ticagrelor administration) activity
- c) after 7-10 days of ticagrelor therapy (phase 2-post-crossover): PK and PD assessment will be assessed to define trough (12 ± 2 hours after last ticagrelor dose) and peak (2 hours after ticagrelor administration) activity.

A flow diagram of the study is presented below.

Blood sampling: Peripheral venous blood samples (20 mL) will be drawn through a short venous catheter inserted into a forearm vein and collected in citrate and serum tubes as appropriate for assessments. The first 2-4 mL of blood will be discarded to avoid spontaneous platelet activation.

Laboratory assessments

1. Whole blood vasodilator-stimulated phosphoprotein (VASP)
2. VerifyNow P2Y12 point of care testing
3. Light-transmittance aggregometry (LTA)
4. Thromboelastography
5. Reticulated Platelets (RPs)

6. Serum thromboxane B2
7. PK assessment

Description of laboratory assays

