In clinical trials, the most common clinical side effects of ticagrelor were dyspnea (13.8%), headache (6.5%), cough (4.9%), dizziness (4.5%), nausea (4.3%), bradycardia (4.4%) principally. Infrequent events included intracranial hemorrhage (0.3%) and severe bradycardia requiring pacemaker insertion (0.9%). Patients considered to be at high risk of bradyarrhythmic events will be excluded. The most important adverse effect associated with the use of ticagrelor is bleeding. The risk of spontaneous bleeding with ticagrelor is 2.8% (24). However, such bleeding prevalence occurred in the setting of long-term (12-15 months) trials, while our study is limited to up to 14 ± 4 days of active treatment thus reducing the risk of bleeding complications. All clinical events described above, if they were to occur, as well as death, MI, stroke, and urgent revascularization procedure with PCI or coronary artery bypass grafting will be recorded. Bleeding data will be collected using PLATO definitions (24). Clinical events will be evaluated by a local committee, comprised of 2 faculty members (2 cardiologists), not directly involved in the research. In the event of a report of a serious adverse event (major bleeding – defined as life-threatening: fatal, symptomatic intracranial hemorrhage, leading to a drop in hemoglobin of at least 5 g/dL, significant hypotension requiring intravenous inotropes, requiring surgical intervention, or requiring transfusion of 4 or more units of blood; non-life-threatening: substantially disabling, intraocular bleeding leading to vision loss, or requiring at least 2 units of blood; thrombocytopenia $<50,000$) the local committee will meet and antiplatelet treatment management will be managed according to physician recommendation.

Definition of Adverse Events

An adverse event is any unintended or undesirable experience that occurs during the course of the clinical investigation whether or not it is considered to be therapy related. This includes any newly occurring event or previous condition that has increased in severity or frequency since the initiation of study treatment. Adverse events will be followed until resolution while the patient remains on-study. Once the patient is removed from study, events thought to be related to the study therapy will be followed until resolution or until the patient starts a new treatment regimen.

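### The platelet-count exclusion is printed 1,000-fold too high for its unit; 80,000/µl is almost certainly meant (minor correction)

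*Combined protocol and SAP*

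**What the plan says.** Among the exclusion criteria listed under Study Population in the combined protocol and SAP is "Platelet count < $80 \times 10^6 / \mu\text{l". The threshold is given once and is not restated anywhere else.

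The criterion is one that staff must apply. The same section assigns screening to the cardiology research staff, "who will verify that all candidates meet inclusion and exclusion criteria", and lets them use blood results up to 90 days old or draw a new sample.

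The only other platelet-count figure is in Possible Discomforts and Risk, where the list of serious events that convene the local committee includes "thrombocytopenia $<50,000". No unit is printed there.

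**The concern.** A cut-off of 80 million platelets per microlitre is not on the scale on which platelet counts are reported, nor on the scale of the document's own thrombocytopenia trigger. The criterion as printed cannot separate patients with a low count from anyone else.

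The study gives a potent antiplatelet drug on top of aspirin, and the protocol names bleeding as its most important adverse effect. A platelet floor is therefore a safety criterion. Under the printed figure no candidate could qualify. Every enrolment would then either breach the protocol or rest on staff silently substituting another number. The Ethical and regulatory section requires deviations to be notified to the IRB, so the written criterion should be the one actually used.

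**Working it through.** This is a unit conversion and an order-of-magnitude check. No sample-size or power formula is involved.

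**Inputs**
- Exclusion limit as printed: 80 × 10⁶ per µl (Exclusion criteria).
- Thrombocytopenia trigger: 50,000, read as per µl (Possible Discomforts and Risk). The unit is an assumption.
- Ordinary adult platelet counts: not in the documents. Assumed to be about 150,000 to 450,000/µl, with 50,000 to 5,000,000/µl tested so that the conclusion does not hang on that assumption.

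**Step 1: the printed value.** 80 × 10⁶/µl = 80,000,000/µl.

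**Step 2: the literal effect.** A patient is excluded if the count is below the limit.

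| Count per µl | Excluded at 80,000,000? | Excluded at 80,000? |
|---|---|---|
| 50,000 | yes | yes |
| 150,000 | yes | no |
| 450,000 | yes | no |
| 1,000,000 | yes | no |
| 5,000,000 | yes | no |

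Even the highest count tested falls short of the printed limit by a factor of 80,000,000 / 5,000,000 = 16.

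**Step 3: candidate corrections.**
- Exponent wrong, unit right: 80 × 10³/µl = 80,000/µl.
- Unit wrong (µl for ml), exponent right: 80 × 10⁶/ml ÷ 1,000 = 80,000/µl.
- Per litre intended: 80 × 10⁶/l ÷ 1,000,000 = 80/µl. This is 50,000 / 80 = 625 times below the document's own thrombocytopenia trigger and is not a workable entry limit.

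The two plausible single slips agree, and the third can be set aside.

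**Step 4: size of the error.** 80,000,000 / 80,000 = 1,000.

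**Step 5: comparison with the document's other limit.** As printed, 80,000,000 / 50,000 = 1,600. As corrected, 80,000 / 50,000 = 1.6. An entry limit somewhat above an adverse-event trigger is reasonable. The remaining gap is not an error, and the two limits need not be equal.

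**The case against.** The strongest objection concerns provenance. The point rests on one exponent and one unit prefix in text that a program extracted from a PDF. A 3 read as a 6, or an m read as µ, would produce exactly this expression, and it would look just as clean. That possibility stands. However, nothing in the text points to a misread: the expression is complete, with no gap, broken table or redaction around it. The right response is to check the source before changing anything.

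The second objection is that the slip is self-evident and harmless. Much of this is true. Screening is done at one centre by cardiology research staff, who would probably recognise it. A literal reading turns patients away and does not admit unsafe ones. Other safeguards exist: "Blood dyscrasia or bleeding diathesis" is a separate exclusion, patients must already have taken aspirin and clopidogrel for at least 30 days, and exposure is short ("maximal treatment period 20 days"). These facts limit the consequence, and hence the rating, but they do not make the printed figure correct.

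Third, the thrombocytopenia trigger has no unit, so it supports the general scale without confirming 80,000 in particular. That is fair. The value of 80,000/µl comes from the agreement of the two single-slip corrections, and the sponsor should confirm it.

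**Conclusion.** The concern holds, as a minor correction. The platelet-count exclusion is wrong as printed by a factor of 1,000. That it would exclude everyone if applied literally rests on assumed platelet counts, but holds across the whole range tested. The inferred limit of 80,000/µl rests on the error being a single slip of exponent or unit. The comparison with the 50,000 trigger rests on that figure being per µl.

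Confidence is medium, because a misread of the PDF cannot be ruled out from the text alone. The primary end point, sample size, randomisation and analysis are unaffected.

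**What to change.** Check the expression against the source PDF. If it is printed there as here, restate the exclusion as a platelet count below 80 × 10³/µl (the same as 80 × 10⁶/ml or 80,000/µl), once the sponsor confirms that value. Make sure any screening form that carries the criterion shows the same figure.

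While the text is open, the unit could be added beside the 50,000 trigger in Possible Discomforts and Risk. That is a convenience and not part of the error.

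The cost is one exponent or unit in the protocol, any matching edit on the screening form, and optionally one added unit. Design and analysis do not change.

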The proposed investigation is a prospective, randomized, cross-over, open-label, PD and PK study in which CAD patients with DM on low-dose (81mg) aspirin and standard-dose (75mg) clopidogrel will be prospectively recruited. Patients will be screened during their regularly scheduled outpatient visits and informed about the study. Patients will be stratified according to CKD status into CKD and non-CKD groups. CKD will be defined according to the functional definition of the KDIGO (Kidney Disease: Improving Global Outcomes) guidelines (CKD: glomerular filtrate rate [GFR] $<60\text{ml}/\text{min}/1.73\text{m}^2$; non-CKD: $\text{GFR} \geq 60\text{ml}/\text{min}/1.73\text{m}^2$) (32,33). The rationale for considering the functional classification to initially stratify patients is in line with clinical studies showing the increased cardiovascular risk and markedly dysfunctional platelets according to GFR strata (10,11,16). For patient stratification, GFR will be estimated through the CKD-EPI (chronic kidney disease epidemiology collaboration) equation, as this is suggested by guidelines as the most accurate method to calculate GFR, especially for values in the normal range (above $60\text{ml}/\text{min}/1.73\text{m}^2$) (32,33). For comparison, GFR will also be calculated with the MDRD (modification of diet in renal disease) equation. In addition, as exploratory analysis, renal function will also be classified according to markers of kidney damage, in

particular albuminuria, in order to obtain a more comprehensive information about CKD (32,33). Albuminuria will be evaluated as albumin-to-creatinine ration (ACR) expressed in mg/g, which is approximately equivalent to albumin excretion rate. According to KDIGO guidelines, CKD will be defined as ACR >30mg/g and non-CKD as ACR ≤30mg/g (32,33). Albuminuria will be measured on random untimed spot urine samples. DM will be defined according to World Health Organization criteria and all subjects with DM will need to be on treatment with oral hypoglycemic agents and/or insulin for at least 2 months without any changes in their regimen (34).

After providing informed consent, eligible patients will be divided into CKD group and non-CKD group as described above. DM patients with CKD or without CKD will be randomized in a 1:1 fashion to one of the following treatment arms:

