- 7) *Pharmacokinetic (PK) assay*: Determination of plasma concentration of ticagrelor and its active metabolite (AR-C124910XX) will be assessed from blood samples taken at the same time points of PD analysis as previously described [40]. Blood samples for measurement of drug concentrations will be drawn through the same cannula used for PD sampling. The blood will be taken into lithium heparin tubes and placed on ice until centrifugation (2800 rpm, 4°C, 10 min) within 30 min of sampling to collect the plasma, which will be transferred to plain polypropylene tubes and frozen upright at or below -20°C until analysis.

Primary and secondary objectives

The primary end point is the level of on-treatment platelet reactivity as assessed by VASP-PRI after treatment with ticagrelor 90mg bid on top of aspirin (81mg/day) for 7-10 days. The primary hypothesis of our study is that in DM patients the presence of CKD is associated with lower platelet inhibition (assessed by PRI determined by VASP-P) compared with those without CKD.

Additional objectives include:

- 1) The comparison of PD measures following administration of ticagrelor 90 mg between CKD and non-CKD groups at each time point assessed with PRU determined by the VerifyNow P2Y12 assay, 5 and 20 µM ADP-induced platelet aggregation by LTA and clot kinetic assessed by CORA[®] system.

- 2) The comparisons of level of platelet reactivity as assessed by multiple assays after treatment with ticagrelor 60 mg bid (on top of aspirin 81mg/day) for 7-10 days between the CKD and non-CKD groups.
- 3) The comparison of plasma concentrations of ticagrelor and its metabolite between the DM patients with and without CKD after 7-10 days of ticagrelor (60 and 90 mg) treatment.
- 4) The comparison of platelet inhibition by standard dose (90mg twice daily) versus low dose (60mg twice daily) of ticagrelor in DM patients with or without CKD.
- 5) The comparison of the rates of high on-treatment platelet reactivity (HPR), defined as VASP-PRI $\geq 50\%$, PRU > 208 , 5 μM ADP-induced maximal platelet aggregation $\geq 46\%$ or ADP induced MA > 47 (41,42).
- 6) To evaluate whether response to ticagrelor varies with the proportion of RPs in DM patients according to the CKD status.
- 7) To assess the effects of different levels of P2Y₁₂ inhibition with thromboxane levels.
- 8) The comparison of PD and PK measures according to the CKD classification based on markers of kidney damage (ACR).

Sample Size Computation and Power Analysis

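### CKD is defined by GFR alone for the primary analysis and by ACR alone for additional objective 8, and that objective, as specified, does not separate albuminuria from low GFR

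*Combined protocol and SAP*

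**What the plan says.** Research design gives two classifications, each resting on one marker.

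- **Primary stratification.** "CKD will be defined according to the functional definition of the KDIGO (Kidney Disease: Improving Global Outcomes) guidelines", with the cut at a GFR of 60 ml/min/1.73m². The non-CKD group carries no ACR condition. A reason is given: "The rationale for considering the functional classification to initially stratify patients is in line with clinical studies" that relate cardiovascular risk and platelet dysfunction to GFR.
- **Second classification.** The protocol adds that, "as exploratory analysis, renal function will also be classified according to markers of kidney damage", and then "CKD will be defined as ACR >30mg/g and non-CKD as ACR ≤30mg/g". This split carries no GFR condition and is attributed to the same guideline.

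The only renal exclusion under Study Population is "Patients with end-stage renal disease on hemodialysis", so patients who are abnormal on one marker and normal on the other can enrol. Additional objective 8 compares PD and PK measures by the ACR classification. The Statistical analysis plan does not mention using GFR and ACR together. It has a general ANCOVA rule that takes as covariates the baseline variables found to differ significantly between groups, and it names neither marker.

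**The concern.** A patient with GFR ≥60 and ACR >30 is non-CKD in the primary analysis and CKD in objective 8. A patient with GFR <60 and ACR ≤30 is the reverse. Every participant has diabetes, and the Background calls diabetes the most common cause of CKD, so discordant patients are to be expected.

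The consequence falls mainly on objective 8. If albuminuria is more common when GFR is low, the ACR >30 group holds more low-GFR patients than the ACR ≤30 group. A difference by ACR could then be the GFR effect under another label. The protocol adds ACR to give a fuller picture of CKD, but re-sorting everyone on ACR alone does not show what ACR adds to GFR.

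There is also a question of interpretation for the primary result. The hypothesis concerns the presence of CKD, so a reader of a null finding will ask whether albuminuric patients in the reference group mattered. No planned analysis addresses this.

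**Working it through.** **Inputs from the documents** (Sample Size Computation and Power Analysis): difference 10 PRI points, common SD 13.0, 37 per group, two-sided α = 0.05, power 90%.

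**Assumed inputs** (the documents give no albuminuria prevalence): a = share with ACR >30 in the GFR <60 group, 40–60%; f = share with ACR >30 in the GFR ≥60 group, 20–30%.

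**1. The plan's own figure.** The two-sample noncentral t calculation for 10/13 at 90% power gives 36.5, so 37 per group. Power at 37 per group is 90.4%. The stated figure reproduces.

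**2. GFR effect leaking into the ACR comparison.** Take equal GFR groups, a 10-point GFR effect and no albuminuria effect. The apparent ACR difference is

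10 × [P(GFR <60 | ACR >30) − P(GFR <60 | ACR ≤30)] = 10 × [a/(a+f) − (1−a)/(2−a−f)].

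| a | f | First share | Second share | Apparent ACR difference |
|---|---|---|---|---|
| 40% | 30% | 0.571 | 0.462 | 1.1 |
| 50% | 30% | 0.625 | 0.417 | 2.1 |
| 40% | 20% | 0.667 | 0.429 | 2.4 |
| 60% | 30% | 0.667 | 0.364 | 3.0 |
| 50% | 20% | 0.714 | 0.385 | 3.3 |
| 60% | 20% | 0.750 | 0.333 | 4.2 |

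The range is 1.1–4.2 points. It is zero if a = f.

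**3. Would the ANCOVA rule correct this?** Only sometimes. With GFR as a two-level variable, 15 of 37 against 11 of 37 (about 40% and 30%) gives a chi-square p of 0.33, so GFR would not enter. With 22 against 7 of 37 (about 60% and 20%), p < 0.001 and it would.

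**4. Direction of any effect on the primary contrast.** Two illustrative models, neither supported nor excluded by the documents:

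- *Shrinking.* Albuminuric patients with GFR ≥60 respond fully like the GFR <60 group, albuminuria adds nothing when GFR is low, and 10 points is read as the difference from patients normal on both markers. The contrast is 10 × (1 − f) = 8 to 7 points, with power 74% to 63%. If those patients carry half the effect, it is 9.0 to 8.5 points, with power 84% to 79%.
- *Enlarging.* Albuminuria adds 5 points at any GFR, on top of a 10-point GFR effect. The contrast is 10 + 5 × (a − f), which is 10.5 (40%, 30%) to 12 (60%, 20%).

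**5. What the proposed analyses could deliver.**

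- The albuminuric GFR ≥60 cell holds 37 × 0.20 = 7.4 to 37 × 0.30 = 11.1 patients, about 7–11.
- The SE of the ACR effect adjusted for GFR group is 13/√[37a(1−a) + 37f(1−f)]. At 40%/20% this is 13/√14.8 = 3.4; at 50%/30% it is 13/√17.02 = 3.2.
- A reference group of GFR ≥60 with ACR ≤30 holds about 30 or 26 patients. Power at 10 points against 37 is 87% or 84%.

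**The case against.** The strongest objection is that the primary analysis has no defect here. The functional definition is named and justified, and under it a patient with GFR ≥60 and albuminuria is correctly non-CKD. The 10-point planning difference is stated for the CKD and non-CKD groups, which are defined by GFR, so it already refers to the groups as enrolled, whatever albuminuria they contain. This stands in full.

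A reader might infer from the overlap that the primary contrast is diluted and the trial underpowered. The documents do not support that. The fall to 74–63% requires re-reading the 10 points as a contrast with patients free of both markers, and assuming that albuminuria matters only when GFR is preserved. An additive model moves the contrast the other way.

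A reader might also infer that the trial cannot tell albuminuria from low GFR. That goes too far: both markers are to be assessed, and the ANCOVA rule may bring GFR in. The fair statement is that the plan does not specify the separation and its covariate rule does not guarantee it.

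Finally, the ACR classification is labelled exploratory, objective 8 is the last of eight additional objectives, and the protocol does not claim that it isolates albuminuria. That limits the importance of the point. It does not remove the case for a comparison that can be interpreted.

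**Conclusion.** The point holds for objective 8. Followed as written, its ACR comparison carries any GFR effect. With a 10-point GFR effect, no albuminuria effect and the assumed shares, the leakage is 1.1–4.2 PRI points; with equal albuminuria in the two GFR groups it is nil.

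The primary analysis is not shown to be flawed, and its 90% power for 10 points between the GFR-defined groups stands. Albuminuria could shrink or enlarge that contrast, and the documents do not settle which. This is an inexpensive improvement to an exploratory objective, together with a useful aid to reading the primary result.

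**What to change.** Keep the GFR-based primary analysis unchanged. Then:

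1. For objective 8, replace the ACR-only comparison with one model containing both GFR group and ACR group. Report the four GFR-by-ACR cell means descriptively.
2. Pre-state a sensitivity analysis of the primary end point comparing the GFR <60 group with patients who have GFR ≥60 and ACR ≤30.

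Both are changes of wording in the analysis plan and use measurements already planned. The cost is imprecision. The smallest cell would hold about 7–11 patients. With an SE of about 3.2–3.4 points, the 95% interval for the adjusted ACR effect would be roughly ±6.5 points, so the model will often leave the question open. The smaller reference group has 84–87% power at 10 points, against 90% for the primary. Both analyses should be presented as supportive.

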Diabetes mellitus (DM) and chronic kidney disease (CKD) represent pandemic diseases and a major public health concerns because of their prevalence and poor cardiovascular prognosis (1-3). DM is the most common cause of CKD and up to 40% of diabetic patients develop CKD (4). CKD was present in approximately one-third of patients with NSTEMI-ACS and was a powerful independent predictor of subsequent mortality (5). Importantly, patients with DM or CKD have a high thrombotic milieu and frequently experience recurrent atherothrombotic events (6-11). Multiple mechanisms may contribute to these observations, including accelerated platelet turnover rates (12,13). These observations underscore the importance of antiplatelet therapy for prevention of atherothrombotic recurrences in these high-risk patients. Clopidogrel is the most widely used platelet P2Y₁₂ receptor inhibitor. However, despite its clinical benefit, patients with DM and CKD frequently experience recurrent atherothrombotic events. The high atherothrombotic recurrence rates in DM and CKD patients are partly due to the inadequate response to antiplatelet agents, in particular clopidogrel, which is enhanced with the co-existence of these disorders (14-17). Therefore, identifying antiplatelet agents with more favorable pharmacokinetic (PK) and pharmacodynamics (PD) profiles is of key importance.

Ticagrelor represents an attractive strategy especially in high-risk patients, such as those with DM and/or CKD (18-20). Ticagrelor, a cyclopentyltriazolopyrimidines, is an oral, reversible, non-competitive P2Y₁₂ receptor inhibitor with rapid onset and offset of action and provides a stronger and more consistent platelet inhibition than clopidogrel (21-23). Although ticagrelor is a direct acting agent, ~30% of its effects are attributed to a metabolite (AR-C124910XX) derived from hepatic metabolism (23). In the large scale phase III PLATO (Platelet Inhibition and Patient Outcomes) trial conducted in ACS patients, ticagrelor, in addition to

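### Trough samples may be drawn 10 to 14 hours after the last dose and no analysis uses the actual time, so a timing difference between the CKD groups, if there is one, would bias the trough contrasts

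*Combined protocol and SAP*

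**What the plan says.** Each ticagrelor phase ends with two samples, described under Research design as "trough (12 ± 2 hours after last ticagrelor dose) and peak (2 hours after ticagrelor administration) activity". For the trough, "patients will not assume their scheduled morning dose of study medication to allow assessment of trough levels of platelet reactivity". The trough clock therefore starts at the previous evening's dose. The protocol does not say where that dose is taken, but these are outpatients, so home is a fair inference. The peak sample differs: "Patients will be administered the dose of the randomized treatment while at the clinic and blood sampling will be collected after 2 hours".

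The Background describes ticagrelor as a "non-competitive P2Y₁₂ receptor inhibitor with rapid onset and offset of action". It gives no half-life and no rate at which platelet reactivity recovers. Drug concentrations "will be assessed from blood samples taken at the same time points of PD analysis as previously described" (pharmacokinetic assay), so they share the trough window.

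Under Primary and secondary objectives, "The primary end point is the level of on-treatment platelet reactivity as assessed by VASP-PRI after treatment with ticagrelor 90mg bid". Neither trough nor peak is named. The secondary objectives compare the other platelet assays and the plasma concentrations between CKD and non-CKD patients. Randomisation is to dose sequence within each CKD group.

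The Statistical analysis plan lists t-tests, Wilcoxon or Mann-Whitney tests, ANOVA, checks of period and sequence effects, and an ANCOVA whose covariates are the baseline variables that differ significantly between groups. Time since dose appears nowhere.

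**The concern.** The window is 4 hours wide, one third of the 12-hour dosing interval. Sampling at both trough and peak presupposes that effect and concentration change within that interval, yet every trough value is analysed as if it were drawn at the same time.

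The window can be enforced only if the time of the last dose is known, so the value should be obtainable. But hours since an on-treatment dose is not a baseline variable, and the ANCOVA rule as written cannot admit it.

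The main contrasts compare CKD with non-CKD patients, and randomisation does not balance dosing or arrival times between those groups. If CKD patients were drawn later on average, their reactivity would look higher and their concentrations lower, which for reactivity is the direction of the primary hypothesis. If they were drawn earlier, a real difference would be partly hidden. For the concentration objective, a timing difference could be read as an effect of CKD on exposure.

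**Working it through.** **Inputs from the documents.** Trough window 12 ± 2 h (Research design). Planned PRI difference 10 points, SD 13.0, 37 patients per group, 90% power, two-sided alpha 0.05 (Sample Size Computation and Power Analysis).

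**Assumptions, not in the documents.** PRI rises 0.5 to 3 points per hour around trough. Half-life is 6 to 12 h. Draw times are uniform over the window.

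**1. The plan's own figure.** The standardised difference is 10/13 = 0.769. A two-sample t-test needs 36.5 per group, rounded up to 37, with power 0.904 at 37. The stated 37 reproduces.

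**2. Timing balanced between groups.** A uniform spread over 4 h has variance 4²/12 = 1.333 h² (SD 1.155 h). The total SD is √(13² + slope² × 1.333).

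| Slope (points/h) | SD | Power at 37 per group |
|---|---|---|
| 0.5 | 13.01 | 0.903 |
| 1 | 13.05 | 0.902 |
| 2 | 13.20 | 0.895 |
| 3 | 13.45 | 0.884 |

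The largest loss is 0.904 − 0.884 = 0.020. There is no bias, and the error rate stays at 5%.

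**3. Timing different between groups.** Bias = slope × difference in mean hours since dose.

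- 0.5 h: 0.5 × 0.5 = 0.25 up to 3 × 0.5 = 1.5 points.
- 1 h: 0.5 × 1 = 0.5 up to 3 × 1 = 3 points.

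Error rates come from a simulation with no true CKD effect, 37 per group and SD 13. Times were uniform on 10 to 14 h, shifted between groups and then clipped to the window, so a nominal 1 h shift becomes about 0.94 h.

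| Nominal shift | Slope 1 | Slope 2 | Slope 3 |
|---|---|---|---|
| 0.5 h, error rate | 0.052 | 0.065 | 0.076 |
| 1 h, error rate | 0.060 | 0.091 | 0.137 |
| 1 h, bias (points) | 0.9 | 1.8 | 2.8 |

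At 0.5 points per hour even the 1 h shift leaves the error rate near 5%. Independent reruns agree within simulation error (up to 0.143 at slope 3). A bias of a full 3 points with SD held at 13 would give 0.165; the simulated figure is lower because clipping reduces the shift and the spread in times raises the SD.

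With a true 10-point difference, a bias of 1, 2 or 3 points towards the null would lower power from 0.904 to 0.836, 0.743 or 0.627.

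**4. Concentrations.** Ratio = 2^(−hours/half-life). For a 1 h mean difference: 2^(−1/12) = 0.944 and 2^(−1/6) = 0.891, so 6% to 11% lower in the group drawn later.

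**5. Effect of adjustment.** With hours since dose in the model and times known exactly, the simulated error rate returns to 0.048 to 0.055 and the bias to about 0. With an assumed 0.75 h reporting error, about 30% of the bias remains (0.3 to 0.9 points at slopes of 1 to 3). If the groups differ by about 1 h, time and CKD status are correlated and the adjusted power for a true 10-point effect is about 84% to 85%.

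**The case against.** The harm needs mean time since dose to differ by CKD status, and the documents give no reason to expect that. Both groups share one centre, common eligibility criteria, a twice-daily regimen, morning sampling with the dose withheld, and the same window. That randomisation does not balance timing is true of any post-baseline variable in a non-randomised comparison. A 1 h shift is also large: 1/1.155 = 0.87 SD of the assumed times, whereas chance imbalance at 37 per group has an SD of only 1.155 × √(2/37) = 0.27 h. All of this stands. It limits the weight of the point but does not remove the omission.

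Three stronger readings are tempting and are not supported.

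- A reader might infer that the primary comparison is biased. The plan does not say whether the primary VASP-PRI is the trough or the peak value. The peak follows a dose given in the clinic, so if the primary value is the peak, this mechanism largely disappears.
- A reader might set the change across the whole window (4 h × 1 to 3 points/h = 4 to 12 points) beside the 10-point target. That is the range for one patient moved from one edge to the other. It would be a group bias only if one group were drawn entirely at 10 h and the other entirely at 14 h.
- A reader might extend the concern to the peak samples and to 90 mg versus 60 mg. No size has been shown for either, and the dose comparison is within patient, so stable habits largely cancel.

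The objection that mandatory adjustment is mere preference stands only in part. A term fixed in advance costs almost nothing when timing is balanced. Tabulating the times without a prespecified model would leave the choice of analysis until after the data are seen.

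**Conclusion.** The omission is real: the plan accepts a 4-hour trough window and has no analysis that can use the actual time. Its consequence is conditional. If mean time since dose differs by 0.5 to 1 h between the CKD groups, the trough PRI contrast is biased by about 0.25 to 3 points against a planned 10, with an error rate of about 5% to 14%. Trough concentrations would be about 6% to 11% lower in the later-drawn group at a 1 h difference. If timing is balanced, the cost is at most about 2 percentage points of power.

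These sizes rest on assumed slopes, half-lives and draw-time distributions, and the documents do not show that the imbalance will occur. The trough secondary and concentration contrasts are exposed in any case; the primary end point is exposed only if it is read at trough. This is a worthwhile refinement of low severity, not a flaw that undermines the design.

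**What to change.** - Record the clock times of the last dose before the visit and of each trough draw.
- Report hours since dose by CKD group.
- Prespecify hours since last dose, centred at 12, as a covariate in the trough CKD versus non-CKD comparisons of VASP-PRI, the other platelet assays and drug concentrations. Include it whether or not it differs between groups, and show the unadjusted result alongside.
- Treat the same adjustment for the peak sample and for 90 mg versus 60 mg as optional.

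No change to dosing, visits or sample size is involved. The cost is two entries per visit on the data sheet and one degree of freedom. The downsides are that self-reported dose times leave some residual bias, that there is little gain when timing is balanced, and that power is lower (about 84% to 85% instead of 90%) if timing differs by about 1 h between the groups.
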